Post-treatment: Participants in the Altitudes condition will be asked to complete the battery of measures examining psychosocial constructs at the approximately 6-month timepoint (+/- 2 weeks). Specifically, Altitudes participants will be asked to complete the Experience of Caregiving Inventory (ECI; Szmukler), the Family Questionnaire of Expressed Emotion (Wiedemann et al., 2002), Brief COPE (Carver, 1997), UCLA Loneliness Scale (Russell, 1996), Multidimensional Scale of Perceived Social Support (For control and Alternative form for Altitudes condition; Zimet et al., 1990), Modified Psychosis Attitudes Survey (PAS; Kopelovich et al., 2022), PTSD Checklist for DSM-5 (PCL-5, Weathers et al., 2013), Post Traumatic Growth Inventory (PTGI, Tedeschi & Calhoun, 1996), General Health Questionnaire-12 (GHQ-12; Goldberg, 1972), Self-Compassion Scale – Short Form (SCS-SF; Raes et al., 2011), Five Facet Mindfulness Scale (FFMQ; Bohlmeijer et al., 2011) and aforementioned Altitudes platform brief questionnaires: the Altitudes Health Care Climate Questionnaire (A-HCCQ), Altitudes Usability Questionnaire (AUQ), and Altitudes Perceived Competence Scale (A-PCS), and Working Alliance Inventory for guided Internet interventions (WAI-I, Gomez Penedo et al., 2019). Participants will complete a brief survey on engagement with services within the CSC program and outside the program (e.g., individual therapy, family groups outside of CSC, etc.). They will also be asked to participate in a qualitative interview focusing on the experience of Altitudes and deeper understanding of acceptability and feasibility of the platform. Participants in the control condition will complete all the aforementioned measures except for the four brief Altitudes questionnaires and the qualitative interview.

Evaluations

Primary outcomes: Our primary objective is to examine the feasibility and acceptability of implementing Altitudes as a part of coordinated specialty care services provided by first-episode psychosis clinics across the state of North Carolina. We will examine site usage information as well as collect data on carers' perceptions of the platform to assess this outcome (e.g., its utility, approachability, and helpfulness).

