Secondary outcomes: Our second aim is to assess the extent to which carers engage with the platform (i.e., site usage information) is associated with improvements in expressed emotion, perceptions of caregiving, coping strategies, loneliness, social support, self compassion, mindfulness, and mood symptoms. We also plan to examine the associations between carers' involvement in Altitudes and their loved one with FEP's use of emergency services (e.g., ED visits). We will compare outcomes from the Altitudes and control groups to examine any improvements experienced by participants who engaged with the platform compared to routine clinical care.

Exploratory outcomes: We would like to explore rates of trauma symptoms related to experiencing and providing support for a loved one who experienced an initial psychotic episode. One of the exploratory aims is to examine the extent to which their loved one's initial psychotic episode and related experiences (e.g., psychiatric hospitalizations, changes in work/school engagement, etc.) might be associated with trauma-related symptoms. We are also interested in the extent to which engagement in Altitudes might promote post traumatic growth among caregivers of a young person with FEP. Trauma and post traumatic growth from caregivers in the treatment group will be compared to controls to assess the extent of impact of Altitudes on these outcomes.

Safety Evaluations

A safety plan for Altitudes was developed before participants joined the digital platform by research staff based on previous experience with digital interventions. All safety measures were approved by the director of each participating NC FEP clinic.

Statistical and Analytic Plan

Primary Outcomes: For Aim 1, we will use descriptive statistics to examine carers' perceptions of the Altitudes platform and clinical moderators via four brief questionnaires: the Altitudes Health Care Climate Questionnaire (A-HCCQ), Altitudes Usability Questionnaire (AUQ), Altitudes Perceived Competence Scale (A-PCS), and Working Alliance Inventory for Guided Internet interventions (WAI-I, Gomez Penedo et al., 2019). Additionally, descriptive statistics will assess interactions with the platform to evaluate acceptability and engagement (e.g., logins, posts, reactions, completed activities, etc.) with the platform (i.e., acceptability and usability).

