To evaluate the extent to which engagement in Altitudes may have impacted treatment participants' psychological health and perceptions of their social environment in comparison to the control group, all individuals will be asked to complete a battery of psychological measures at baseline, mid-treatment, and post-treatment visits. All measures will be administered by a member of the study team via secure Zoom. They will additionally complete a brief engagement measures on services they are accessing (e.g., services through the CSC program, individual therapy, group therapy at an outside organization, etc.).

At each of the three timepoints, all participants will be asked to complete the Experience of Caregiving Inventory (ECI; Szmukler), the Family Questionnaire of Expressed Emotion (Wiedemann et al., 2002), Brief COPE (Carver, 1997), UCLA Loneliness Scale (Russell, 1996), Multidimensional Scale of Perceived Social Support (For control and Alternative form for Altitudes condition; Zimet et al., 1990), Modified Psychosis Attitudes Survey (PAS; Kopelovich et al., 2022), PTSD Checklist for DSM-5 (PCL-5, Weathers et al., 2013), Post Traumatic Growth Inventory (PTGI, Tedeschi & Calhoun, 1996), General Health Questionnaire-12 (GHQ-12; Goldberg, 1972), Self-Compassion Scale – Short Form (SCS-SF; Raes et al., 2011), and Five Facet Mindfulness Scale (FFMQ; Bohlmeijer et al., 2011).

At baseline, all participants will be asked to complete a brief demographic questionnaire and answer a small number of clinical questions about their loved one (e.g., "Of the options provided below, what stage of recovery best describes your loved one?").

At midpoint, Altitudes condition participants will also be asked to provide their perceptions of the Altitudes platform and clinical moderators via four brief questionnaires: the Altitudes Health Care Climate Questionnaire (A-HCCQ), Altitudes Usability Questionnaire (AUQ), and Altitudes Perceived Competence Scale (A-PCS) and Working Alliance Inventory for guided Internet interventions (WAI-I, Gomez Penedo et al., 2019).

At posttreatment, Altitudes condition participants will be asked to participate in a qualitative interview focusing on the experience of Altitudes and deeper understanding of acceptability and feasibility of the platform.

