With approval from the IRB & clinic directors, the research time will post flyers with a description of the study and eligibility criteria in the clinic waiting rooms to allow for caregivers to self-refer and/or to enable clients with FEP to share information about the study with their loved ones. If individuals self-refer (in response to flyers), the RA and PI will consult with the treatment team first before screening the individual (i.e., to confirm their loved one is currently receiving or recently graduated from the CSC program).

Baseline Procedures

The study coordinator will meet virtually with prospective participants for about 1 hour to complete all baseline measures. The demographic form will be completed first, which collects basic information about sex, age, ancestry, education, current zip code, and basic information on their loved one, including their loved one age, duration of illness, and length of time in the CSC program. After completing these documents, the study coordinator will guide participants through virtual copies of the demographic questions and psychological measures, including the Experience of Caregiving Inventory (ECI; Szmukler), the Family Questionnaire of Expressed Emotion (Wiedemann et al., 2002), Brief COPE (Carver, 1997), UCLA Loneliness Scale (Russell, 1996), Multidimensional Scale of Perceived Social Support (For control and Alternative form for Altitudes condition; Zimet et al., 1990), Modified Psychosis Attitudes Survey (PAS; Kopelovich et al., 2022), PTSD Checklist for DSM-5 (PCL-5, Weathers et al., 2013), Post Traumatic Growth Inventory (PTGI, Tedeschi & Calhoun, 1996), General Health Questionnaire-12 (GHQ-12; Goldberg, 1972), Self-Compassion Scale - Short Form (SCS-SF; Raes et al., 2011), and Five Facet Mindfulness Scale (FFMQ; Bohlmeijer et al., 2011). Additionally, all participants will complete a brief survey on engagement with services within the CSC program and outside the program (e.g., individual therapy, family groups outside of CSC, etc.).

For Altitudes participants only, once all baseline study measures are complete, the study coordinator will conduct a 20- to 30-minute orientation of the Altitudes platform, including creation of an Altitudes profile and orientation to the features of the site. All participants will be compensated \$20.00/hour prorated to the nearest half hour for completion of this visit and their time.

Intervention Period Procedures

Mid-Treatment Procedures

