The study coordinator will meet virtually with all participants for approximately 30 minutes to complete the mid-treatment measures. All participants will complete virtual copies of the Experience of Caregiving Inventory (ECI; Szmukler), the Family Questionnaire of Expressed Emotion (Wiedemann et al., 2002), Brief COPE (Carver, 1997), UCLA Loneliness Scale (Russell, 1996), Multidimensional Scale of Perceived Social

Support (For control and Alternative form for Altitudes condition; Zimet et al., 1990), Modified Psychosis Attitudes Survey (PAS; Kopelovich et al., 2022), PTSD Checklist for DSM-5 (PCL-5, Weathers et al., 2013), Post Traumatic Growth Inventory (PTGI, Tedeschi & Calhoun, 1996), General Health Questionnaire-12 (GHQ-12; Goldberg, 1972), Self-Compassion Scale – Short Form (SCS-SF; Raes et al., 2011), and Five Facet Mindfulness Scale (FFMQ; Bohlmeijer et al., 2011). Additionally, all participants will complete a brief survey on engagement with services within the CSC program and outside the program (e.g., individual therapy, family groups outside of CSC, etc.). At midpoint, Altitudes participants will also be asked to provide their perceptions of the Altitudes platform and clinical moderators via four brief questionnaires: the Altitudes Health Care Climate Questionnaire (A-HCCQ), Altitudes Usability Questionnaire (AUQ), and Altitudes Perceived Competence Scale (A-PCS) and Working Alliance Inventory for guided Internet interventions (WAI-I, Gomez Penedo et al., 2019). All participants will be compensated \$20.00/hour prorated to the nearest half hour for completion of this visit and their time.

Post-Treatment Procedures

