The study coordinator will meet virtually with family and support participants for approximately 1-1.5 hours to complete the post-treatment measures; however, visits for control participants is likely to be closer to a half hour. All participants will complete virtual copies of the Experience of Caregiving Inventory (ECI; Szmukler), the Family Questionnaire of Expressed Emotion (Wiedemann et al., 2002), Brief COPE (Carver, 1997), UCLA Loneliness Scale (Russell, 1996), Multidimensional Scale of Perceived Social Support (For control and Alternative form for Altitudes condition; Zimet et al., 1990). Modified Psychosis Attitudes Survey (PAS; Kopelovich et al., 2022), PTSD Checklist for DSM-5 (PCL-5, Weathers et al., 2013), Post Traumatic Growth Inventory (PTGI, Tedeschi & Calhoun, 1996), General Health Questionnaire-12 (GHQ-12; Goldberg, 1972), Self-Compassion Scale – Short Form (SCS-SF; Raes et al., 2011), and Five Facet Mindfulness Scale (FFMQ; Bohlmeijer et al., 2011). Additionally, all participants will complete a brief survey on engagement with services within the CSC program and outside the program (e.g., individual therapy, family groups outside of CSC, etc.). After completing these virtual measures, the study coordinator will lead Altitudes participants only through a feedback survey and individual feedback interview regarding the Altitudes platform, their online therapist, the Family PSS, and the community newsfeed. Altitudes participants will be welcomed to share their opinions regarding their experience, including suggestions for how to improve Altitudes in the future. All participants will be compensated \$20.00/hour prorated to the nearest half hour for completion of this visit and their time.

DATA ANALYTIC PLAN

Primary Outcome Measures*

- *Primary outcomes solely apply to those in the Altitudes condition
 - 1. Qualitative Summaries of Participant Experience in Post-Treatment Feedback [Time Frame: up to 6 months]
 - This qualitative data will be collected post-treatment from Altitudes participants. Individual interviews will discuss usage of the platform and any feedback participants may have. Feedback from participants will be summarized to include

common themes regarding likes and dislikes of the platform, implementation within the clinical setting, and participant ideas for future directions.

2. Quantitative Summaries of Participant Experience in Post-Treatment Feedback [Time Frame: up to 6 months]

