This quantitative data will be collected post-treatment from Altitudes participants. Feedback forms will prompt participants to answer questions regarding their experience with the platform on a scale of 1 to 5, with higher scores reflecting a more positive experience. Frequency counts will be included here.

3. Mean change in Working Alliance Inventory for Guided Internet Interventions (WAI-I) – Total Score [Time Frame: Mid-treatment, post-treatment, up to 6 weeks]

The Working Alliance Inventory for Guided Internet Interventions (WAI-I) is a 12-item scale. Answers are on a 5-point scale with options "seldom", "sometimes", "fairly often", "very often", and "always". Possible scores are averaged across items and range from 1 to 5. Higher scores indicate greater therapeutic alliance.

4. Mean change in Working Alliance Inventory for Guided Internet Interventions (WAI-I) – Task and goals subscale [Time Frame: Mid-treatment, post-treatment, up to 6 weeks]

The Working Alliance Inventory for Guided Internet Interventions (WAI-I) task and goals subscale is an 8-item scale. Answers are on a 5-point scale with options "seldom", "sometimes", "fairly often", "very often", and "always". Possible scores are averaged across items and range from 1 to 5. Higher scores indicate greater agreement between the therapist and client on tasks and goals.

5. Mean change in Working Alliance Inventory for Guided Internet Interventions (WAI-I) – Bond subscale [Time Frame: Mid-treatment, post-treatment, up to 6 weeks]

The Working Alliance Inventory for Guided Internet Interventions (WAI-I) is a 4-item scale. Answers are on a 5-point scale with options "seldom", "sometimes", "fairly often", "very often", and "always". Possible scores are averaged across items and range from 1 to 5. Higher scores indicate stronger bond with the supporting therapist

6. Mean change in Perceived Autonomy Support Scale – Total Score [Time Frame: Mid-treatment, post-treatment, up to 6 weeks]

The Perceived Autonomy Support Scale is a 6-item scale. Answers are on a 7-point scale ranging from "strongly disagree", "moderately disagree", "slightly disagree", "neutral", "slightly agree", "moderately agree", and "strongly agree". Possible scores are averaged across all 6 items. Higher scores indicate greater global support of client autonomy from the treatment provider or team.

Secondary Outcome Measures

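### Primary outcomes 3-6 are defined as mid-to-post change, which cannot show whether alliance or autonomy support was good; the analysis text, visit lists and time frames do not match that definition

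*Combined protocol and SAP*

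**What the plan says.** **Outcome list.** Data Analytic Plan, Primary Outcome Measures, gives outcome 3 as "Mean change in Working Alliance Inventory for Guided Internet Interventions (WAI-I) – Total Score [Time Frame: Mid-treatment, post-treatment, up to 6 weeks". Outcomes 4 and 5 (the two WAI-I subscales) and outcome 6 (Perceived Autonomy Support Scale) have the same form and time frame. A note adds: "Primary outcomes solely apply to those in the Altitudes condition".

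**Baseline.** Neither instrument is in the baseline lists of the synopsis or of Baseline Procedures. The latter introduces the platform afterwards: "once all baseline study measures are complete, the study coordinator will conduct a 20- to 30-minute orientation of the Altitudes platform".

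**Analysis text.** The synopsis, Statistical and Analytic Plan, Primary Outcomes, says: "For Aim 1, we will use descriptive statistics to examine" carers' perceptions on the A-HCCQ, AUQ, A-PCS and WAI-I. It does not restrict this to change, gives no time point and does not name the Perceived Autonomy Support Scale.

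**Visit lists.** At mid-treatment the sources agree: "At midpoint, Altitudes participants will also be asked to provide their perceptions of the Altitudes platform and clinical moderators via four brief questionnaires". At post-treatment they do not. The synopsis lists the four questionnaires at about 6 months and confirms this by exempting controls: "Participants in the control condition will complete all the aforementioned measures except for the four brief Altitudes questionnaires and the qualitative interview". The Overview under Research Design & Methods adds only the interview: "At posttreatment, Altitudes condition participants will be asked to participate in a qualitative interview". Post-Treatment Procedures gives the shared battery and the service survey, and then: "After completing these virtual measures, the study coordinator will lead Altitudes participants only through a feedback survey and individual feedback interview".

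**Time frames.** Outcomes 3-6 carry a limit of 6 weeks. Six secondary outcomes (UCLA Loneliness, social support, ECI, Family Questionnaire, GHQ-12, Brief COPE) and two exploratory ones (PCL-5, PTGI) name the post-treatment visit with a limit of 14 weeks.

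**The concern.** The primary aim is feasibility and acceptability, and the hypothesis under Outcomes is that carers will find the platform useful. Those are statements about level. A change between two visits that both fall after onboarding measures drift: a stable poor alliance and a stable good one give the same result. It also needs both values from each carer, so with at most 30 Altitudes participants, someone who answers only at mid-treatment adds nothing to it.

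The second concern is collection. Staff who work from Post-Treatment Procedures as written would not administer the WAI-I at that visit, and outcomes 3-5 could then not be computed. For outcome 6 neither value has a named source, unless the Perceived Autonomy Support Scale is the A-HCCQ under another name. The documents do not say so.

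**Working it through.** The plan gives no power calculation or target value for these outcomes, so there is no figure of its own to reproduce. The check is a comparison of the sections plus short arithmetic.

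**1. How many instruments.** The WAI-I has 12 items: 8 task and goals, 4 bond. With item-mean scoring, total = (8 x task/goals + 4 x bond)/12 = 2/3 task/goals + 1/3 bond. Outcome 3 is therefore fixed by outcomes 4 and 5. Outcomes 3-6 are four of the six primary entries but two instruments.

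**2. What a change score leaves open.** The WAI-I runs from 1 to 5. If the mean change is d >= 0, the post-treatment mean lies in [1 + d, 5], a width of 4 - d out of 4.

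| Mean change d | Possible post-treatment mean | Share of the range |
|---|---|---|
| 0 | 1 to 5 | 4.0/4 = 100% |
| +0.5 | 1.5 to 5 | 3.5/4 = 87.5% |
| +1.0 | 2 to 5 | 3.0/4 = 75% |

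For example, means of 1.5 then 1.5, and of 4.5 then 4.5, both give 0. Means of 1.2 then 2.0 give +0.8 with a low level; 4.8 then 4.6 give -0.2 with a high one. This is a property of any difference score, not an estimate for this trial. The same logic applies to the 7-point autonomy scale.

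**3. Where each value would come from.**

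| Source | WAI-I mid | WAI-I post | Perceived Autonomy Support Scale |
|---|---|---|---|
| Primary Outcome Measures | yes | yes | mid and post |
| Synopsis visit lists | yes | yes | not named |
| Overview | yes | not named | not named |
| Mid- and Post-Treatment Procedures | yes | not named | not named |

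The feedback survey in Post-Treatment Procedures cannot be assumed to contain the WAI-I. The feedback form is a separate primary outcome (number 2) from the WAI-I entries, and the Treatment period text calls it optional.

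**4. Time frames against the visits.** The synopsis gives about 3 and 6 months, each +/- 2 weeks. The Treatment period text gives weeks 10-14 and week 24.
- With 4-week months: 12 +/- 2 = 10-14, and 24 +/- 2 = 22-26.
- With calendar months (13.0 and 26.1 weeks): 11.0-15.0, and 24.1-28.1.
- The earliest mid-treatment visit on any reading is week 10; the earliest post-treatment visit is week 22.
- The 6-week limit ends 10 - 6 = 4 weeks before mid-treatment and 22 - 6 = 16 weeks before post-treatment (24 - 6 = 18 with week 24).
- The 14-week limit ends 22 - 14 = 8 weeks before post-treatment (24 - 14 = 10 with week 24).
- Read as the interval between the visits, 6 weeks still fails, because the shortest interval is 22 - 14 = 8 weeks.

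**The case against.** The strongest reply is that the synopsis already plans descriptive statistics, under its Primary Outcomes heading, on four questionnaires that include the WAI-I. A reader might infer from the outcome list that levels will never be reported. The documents do not support that: a descriptive summary would normally include the mean at each visit. What remains is that the two sections define the primary result differently, that the synopsis gives no time point, and that it leaves out the Perceived Autonomy Support Scale.

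A reader might also infer that the WAI-I is dropped at post-treatment. That too goes beyond the text. The synopsis schedules it, the exemption for controls confirms the intention, and the outcome list names the visit. The Overview and Post-Treatment Procedures are silent; they do not exclude it. The feedback survey covers the online therapist and is also rated 1-5, so some overlap in content is possible. The separate outcome entry still speaks against treating the two as one. The objection shows that the intention is clear, but not that the working procedure carries it out.

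Finally, this is a descriptive pilot, and no sample size or error rate is affected. That is correct and limits the weight of the point.

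**Conclusion.** The point stands as a defect of definition and consistency that should be fixed. As listed, four of the six primary entries, from two instruments, cannot show whether alliance or autonomy support was good. The outcome list does not match the synopsis analysis text. If Post-Treatment Procedures is followed literally, the second WAI-I value is not collected. Outcome 6 has no named source at either visit unless it is the A-HCCQ.

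It would be too strong to say that the primary aim cannot be answered: primary outcomes 1 and 2 and the site usage data also address it. Nor do the 6- and 14-week limits mean that data are lost. They are labelling errors on 4 primary, 6 secondary and 2 exploratory outcomes.

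The conclusion rests on reading mean change with two named visits as the difference between them, and on treating an unnamed questionnaire as not guaranteed to be given.

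**What to change.** 1. Define outcomes 3-6 as the level (mean, SD, n) at mid-treatment and at post-treatment, with mid-to-post change as supporting description. State the same time points in the synopsis analysis text.
2. Name the A-HCCQ, AUQ, A-PCS and WAI-I in the post-treatment text of the Overview and of Post-Treatment Procedures, as the synopsis does.
3. State whether the Perceived Autonomy Support Scale is the A-HCCQ; if it is not, add it to the visit lists and to the Aim 1 analysis text.
4. Replace the 6- and 14-week limits with time frames that cover the named visits, for example the 6 months used for primary outcomes 1 and 2 plus the visit window.

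**Cost.** A protocol amendment: the Protocol Amendments section requires IRB approval for changes to outcomes and analysis. No new visit is needed, because the synopsis already plans the four questionnaires at post-treatment. Time looks sufficient but is approximate. The mid-treatment visit, with the shared battery and the four questionnaires, is put at about 30 minutes and the interview at about 45. Together that is 75 minutes against a planned 60-90, which leaves at most 15 for the feedback survey. Controls, who complete no platform questionnaires, are also expected to need about half an hour at post-treatment, so the spare time should not be relied on.
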